6.6 Alternatives

Alternative therapies include chemotherapy alone, standard chemotherapy/radiation, surgical re-exploration with possible re-resection, palliative symptomatic relief, or no further treatment. Additionally, patients may choose to receive treatment to improve quality of life but that may have no effect on the growth of their cancer. The risks of chemotherapy and standard chemotherapy/radiation include nausea, vomiting, diarrhea, fatigue, bone marrow suppression, and sepsis. The potential benefits of chemotherapy or standard chemotherapy/radiation are prolonged survival. The risk of pursuing no further treatment is tumor progression or spread.

6.7 Compensation

Subjects will not be paid to participate in the study.

7. ADVERSE EVENTS: LIST AND REPORTING REQUIREMENTS

7.1 Adverse Events and Potential Risks List

Based upon our prior phase I and phase II studies evaluating the toxicities associated with Linac based SBRT for pancreatic cancer, we estimate that $\leq 20\%$ of patients will experience grade 2 or higher late GI toxicity within one year. Late GI toxicities are those events occurring more than 3 months after Linac based SBRT. Acute GI toxicities are those events occurring within 3 months following Linac based SBRT. The major toxicity in this group of patients is the development of duodenal/gastric ulcers. Most of these are successfully managed medically. However, Stanford has observed 2 cases of duodenal perforation associated with Linac based SBRT. We anticipate that because of refinements in radiation treatment planning techniques and because the dose will be divided over five treatments (as opposed to one), the biological equivalent and actual dose to the duodenum will be less than prior studies. We anticipate that the risk of ulcer formation should be lower in this study. Hepatic and renal toxicity is not anticipated given the expectation of limited incidental irradiation of these organs and we have not observed any to date in the patients treated with Linac based SBRT. Complications, if any, will be graded according to the RTOG Gastrointestinal Toxicity Scale and/or CTCAE v4.0.

7.2 Reporting of Serious of Unexpected Adverse Events

- 7.2.1 All **fatal** events, both **anticipated and unanticipated**, must be reported to the JHM IRB within a time period as specified by current institutional guidelines after the PI learns of the event, whether or not the PI believes the event to be related to the study. All other events, which are both **serious** and **unanticipated**, must be reported to the JHMI IRB within a time period as specified by current institutional guidelines after the PI learns of the event. Events which are **serious** but **anticipated**, should be reported as part of the continuing review application. If any of these Serious Adverse Events requires a change to the protocol or consent form, the PI must make those changes promptly and submit the revised documents to the JHM IRB.
- 7.2.2 **Important** Adverse Events that are **unanticipated** must be reported to the JHM IRB within a time period as specified by current institutional guidelines. If the Important Adverse Event requires changes to the protocol or consent form, the PI must make those changes promptly and submit the revised documents to the JHM IRB.
- 7.2.3 All other **unanticipated** Adverse Events or changes to the protocol and consent form must be reported to the JHM IRB, within a time period as specified by current institutional guidelines

Addendum (8/15/2014):

Adverse events will be recorded using Mosaiq software, Low grade toxicities are to be expected given the disease profile. Any toxicity below CTCAE v4.0 grade 3 will not be reported on the Master AE Log or Case Report Forms. However, this information will be retained in patient charts.

Towards end of life, hospitalization events increase within this patient population. Hospitalizations that occur greater than 30 days from completion of SBRT and that are not attributable to research intervention will be recorded on the Master AE Log and reported at the time of continuing review and SMC monitoring.

These parameters are drafted in accordance with CFR21, though provide realistic expectations based on the sickness of this patient population.

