12.2 Stopping Rules

All outcome data (toxicity and efficacy) will be reviewed every 6 months by the Principal Investigator and key Co-Investigators. This study will be monitored by the JHH IRB. All potential adverse events will be reported to the SKCCC Data Safety Monitoring Committee and the JHH IRB. An interim analysis is planned to assess late grade 2 or greater gastritis, enteritis, fistula, ulcer, or late grade 3 or greater GI toxicity when 16 patients are accrued. If 7 or more patients have late grade 2 or greater gastritis, enteritis, fistula, ulcer, or late grade 2 or greater gastritis, enteritis, fistula, ulcer, or late grade 2 or greater gastritis, enteritis, fistula, ulcer, or late grade 3 or greater GI toxicity within one year, the trial will be halted (note: accrual will continue while interim analysis is being conducted). After the first 16 patients are followed up for one year, we will also estimate the 1-year local progression free survival. If the upper bound of a two-sided 98% confidence interval (alpha = 0.02) of local progression free survival is below 30% in cohort A, or less than 50% in cohort B, the accrual at that cohort will be halted for lack of efficacy.

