13. STATISTICAL CONSIDERATIONS

13.1 Endpoints

13.1.1 Primary Endpoint

To evaluate late (>3 months after Linac based SBRT) grade 2 or greater gastritis, fistula, enteritis, or ulcer, or any other grade 3 or greater gastrointestinal toxicity attributable to fractionated Linac based SBRT.

- 13.1.2 Secondary Endpoints
 - To determine rates of local progression free survival, overall survival, metastasis-free survival, and progression-free survival at 3, 6, and 12 months from Linac based SBRT.
 - To evaluate acute toxicity, defined as any grade 3 or greater gastrointestinal toxicity within 3 months of treatment.
 - To use FDG-(if available as per the recommendation by your treating physician) /CT scans for assessment of tumor response and progression.
 - To evaluate the role of FDG-PET scans in treatment planning.
 - To assess the quality of life before and after fractionated Linac based SBRT.
 - To further standardize Linac based SBRT delivery and dosimetric parameters.
 - To compare toxicity and outcomes among patients treated with fractionated Linac based SBRT delivered as 5 Gy x 5 (Cohort A of current protocol), 6.6 Gy X 5 (Cohort B of current protocol), 25 Gy X 1 (previous study), and 5-10 Gy x 3 (previous study).
 - To evaluate pain control (as define by pain medication requirements at 3, 6, and 12 months following Linac based SBRT.

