The sample size is 60 patients per cohort. The primary outcome used to determine the sample size is the percentage of individuals with a late gastrointestinal toxicity (grade 2-4) at one year. The late grade 2 or greater toxicity rates was previously observed for other treatment regiments for locally advanced pancreatic cancer were approximately 40%. We hypothesize that in each cohort, the toxicity rate for this regimen will be 20%, a 50% reduction. The stopping rules for futility were calculated based upon a two-stage design with a total sample size of 60 and an interim analysis of 16 patients (note: accrual will continue while interim analysis is being conducted). Within 16 patients, if 7 or more patients have late grade 2 or greater gastritis, enteritis, fistula, ulcer, or late grade 3 or greater GI toxicity, the trial will be stopped. If 6 or fewer patients have late grade 2 or greater gastritis, enteritis, fistula, ulcer, or late grade 3 or greater GI toxicity, then the study will continue enrolling patients until 60 patients have been accrued. After 60 patients are enrolled, if 17 or more of the patients have late grade 2 or greater gastritis, enteritis, fistula, ulcer, or late grade 3 or greater GI toxicity, the null hypothesis will not be rejected. If 16 or fewer of the patients have late grade 2 or greater gastritis, enteritis, fistula, ulcer, or late grade 3 or greater GI toxicity, we will conclude that one year late toxicity is below 40%. This design will reach 91% power with 2% type I error for grade 2 or greater late toxicity, and the probability of early termination is 0.47. In addition, this sample size will reach 89% and 90% power to test the increase of 1-year local progression free survival from 30% to 45% in cohort A and 50% to 65% in cohort B, respectively.

The calculation is based on a one-sided test at significance level 0.04, assuming exponential distribution for local progression time and 2.5 year uniform accrual time with 1 year follow up.

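### The 2014 addendum keeps toxicity below grade 3 off the CRFs and AE log, does not exempt the late grade 2 events in the primary endpoint, and no section names the record behind the two toxicity counts

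*Combined protocol and SAP*

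**What the plan says.** The addendum dated 8/15/2014 in Section 7.2 is current text. It has adverse events recorded in Mosaiq and then sets a grade floor for the trial's forms: "Any toxicity below CTCAE v4.0 grade 3 will not be reported on the Master AE Log or Case Report Forms". It adds: "However, this information will be retained in patient charts". It lists no exception.

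The primary endpoint in Section 13.1.1 is late "grade 2 or greater gastritis, fistula, enteritis, or ulcer, or any other grade 3 or greater gastrointestinal toxicity attributable to fractionated Linac based SBRT". Both toxicity rules use the same grade 2 terms:

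- **Interim (12.2, repeated in 13.4.2):** "If 7 or more patients have late grade 2 or greater gastritis, enteritis, fistula, ulcer", or other late GI toxicity of grade 3 or more, "within one year, the trial will be halted".
- **Final (13.4.2):** "If 16 or fewer of the patients have late grade 2 or greater gastritis, enteritis, fistula, ulcer", or other late GI toxicity of grade 3 or more, leads to the conclusion that the one-year rate is below 40%.

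Sections 13.3 and 13.6 plan toxicity tables by type and grade, with no lower limit. Section 12.2 also says: "All potential adverse events will be reported to the SKCCC Data Safety Monitoring Committee and the JHH IRB"; Section 13.3 repeats this.

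Other sections give grade 2 events a general route. Section 6.2.5 grades complications by CTCAE v4.0 and uses the RTOG scale as well (7.1 words this as and/or). The study calendar (Section 10) schedules an AE evaluation at every follow-up, by telephone if needed. Section 12.1.2 lists follow-up toxicities among the data entered into Oncospace, either from source documents or from CRFs.

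**The concern.** For most low-grade toxicity the addendum is sensible relief from paperwork. For gastritis, enteritis, fistula and ulcer it is not, because grade 2 is where the primary endpoint begins. Staff who follow the addendum to the letter keep part of that endpoint off the CRFs and the Master AE Log. Staff who follow Section 12.1.2 may enter the same event into Oncospace from the chart. Both comply with the protocol, and no section says which record the two counts use.

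An affected patient who is missed can only lower the toxicity count, so the error runs one way: away from the interim halt and toward concluding that the rate is below 40%. The cut-offs leave little room, so a few missed patients per cohort would matter.

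**Working it through.** **Inputs (13.4.2).** Per cohort: 16 patients at the interim, stop at 7 or more; 60 in total, success at 16 or fewer; null rate 40%, alternative 20%. Stated properties: type I error 2%, power 91%, probability of early termination 0.47.

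**Formulas.** With X ~ Bin(16, p) and Y ~ Bin(44, p):

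- Stop(p) = P(X ≥ 7)
- Success(p) = Σ over x = 0 to 6 of P(X = x) · P(Y ≤ 16 − x)

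**The plan's own figures.** Stop(0.40) = 0.4728, Success(0.40) = 0.0209 and Success(0.20) = 0.9076. All three stated figures reproduce. They assume that every affected patient is counted, including those whose only qualifying event is grade 2.

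**A fixed number missed, true rate 40%.** A missed patient is one with no captured qualifying event.

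At the final count, with the interim count complete, missing k affected patients turns the success limit into a true total of 16 + k. The probabilities of continuing and having a true total of 17, 18 or 19 are 0.0172, 0.0263 and 0.0368. False success is therefore:

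- k = 1: 0.0209 + 0.0172 = 0.0381
- k = 2: 0.0381 + 0.0263 = 0.0644
- k = 3: 0.0644 + 0.0368 = 0.1012

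At the interim, missing one affected patient means that 8 true cases are needed to stop. Since P(X = 7) = 0.1889, the stopping probability becomes 0.4728 − 0.1889 = 0.2839.

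**A fraction m of affected patients missed at both looks.** The recorded rate is 0.40 × (1 − m).

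| m | Recorded rate | False success | Interim stop |
|---|---|---|---|
| 0 | 0.40 | 0.021 | 0.473 |
| 5% | 0.38 | 0.042 | 0.407 |
| 10% | 0.36 | 0.079 | 0.343 |
| 20% | 0.32 | 0.219 | 0.226 |

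False success reaches 5% at a recorded rate of 0.3747, so m = 1 − 0.3747/0.40 = 6.3%, or 1.5 of the 24 affected patients expected in 60. It reaches 10% at 0.3516, so m = 12.1%, or 2.9 of 24.

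**Rescaling to the patients exposed.** The addendum does not touch a patient who also has a qualifying grade 3 or greater event, because that event is still logged. So m must be divided by the share of affected patients whose qualifying events are all grade 2. The plan does not give that share. Two earlier single-fraction studies it describes suggest a range: (7 − 2)/7 = 71% (Section 3.2) and 4/(4 + 9) = 31% (Section 3.3). Neither is restricted to the four endpoint terms, so both are assumptions. The 5% threshold then means missing 0.063/0.714, about 9%, to 0.063/0.308, about 21%, of the grade-2-only patients. The 10% threshold means about 17% to 39%.

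**The case against.** The best defence is that the addendum limits safety paperwork and not endpoint data. It sits in a section on reporting serious or unexpected events, has adverse events recorded in Mosaiq with no grade floor, and keeps the low-grade information in charts. Grading is required, AE evaluation is scheduled at each follow-up, and Section 12.1.2 allows entry into Oncospace straight from source documents. Section 12.2 plans the interim analysis specifically to assess these events and adds: "All outcome data (toxicity and efficacy) will be reviewed every 6 months by the Principal Investigator and key Co-Investigators". If those routes are used, every grade 2 event can be found and the stated error rates stand.

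Much of this holds, and it rules out two stronger readings:

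- A reader might infer that all grade 2 endpoint events are lost. With the 31% and 71% shares, a true 40% rate would then appear as 27.7% or 11.4%, and false success would be 0.477 or 0.999. The documents do not support this, because the events remain recorded and recoverable.
- A reader might infer from the wording of 7.1 that an event graded only on the RTOG scale falls outside the addendum's CTCAE cut-off. Section 6.2.5 calls for CTCAE grading with RTOG in addition, so that gap is not established.

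The defence does not remove the conflict. The addendum names the CRFs as well as the AE log. The routes around it are general: none exempts the four terms, and none is named as the source for the 7/16 or 16/60 count.

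**Conclusion.** The point holds as a conflict in the text over primary endpoint data: a stated rule keeps part of the endpoint off the CRFs, and no section says where the two counts come from. This rests on the wording alone and needs no assumption about losses.

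The direction of any resulting error is certain; its size is not. The error rates above illustrate assumed misses at a true 40% rate, and the grade shares are borrowed from other regimens. The documents give no loss rate, and it may be zero. The margin is nonetheless thin: two missed patients in a cohort at the final count are enough to take false success past 5%. Because the endpoint drives the halt and the conclusion in each cohort, and the correction is cheap, it should be made before either rule is applied.

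**What to change.** Add one exception to the addendum: grade 2 gastritis, enteritis, fistula and ulcer are recorded, with CTCAE grade and onset date, on the CRF or in a dedicated Oncospace field. One record is enough.

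Name that record as the source for the 7/16 and 16/60 patient counts in each cohort. Apply the definition of late as more than three months (synopsis, 7.1, 13.1.1) and the one-year window (12.2, 13.4.2).

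Before each rule is applied, back-fill patients already treated from charts, Mosaiq and the records requisitioned from local providers under Section 6.4.

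**Cost.** A short amendment, a few data fields, and chart abstraction that includes retrospective grading and dating, some of it from outside records. No new visits or patients. The addendum's relief for other low-grade toxicity stays in place.

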12.1.2 Data Entry and Compilation

Research Staff (Coordinators, Nurse, or Co-Investigators) will enter/scan subject data into Oncospace, which will include:

- Eligibility or Inclusion/Exclusion Criteria
- Patient Demographics
- Pre-Study Evaluation including H & P, Allergies, and Review of Systems
- Surgical Procedures, with dates and findings (including EUS, biopsy (if needed), seed placement, and/or stent (if recommended)
- Scan dates (PET/CT (if available) and/or CT)
- Treatment planning date
- Pre-Study Labs including hematology, chemistry, and tumor markers (CBC, CMP and CA 19-9)
- Radiation therapy dates and toxicities reported
- Follow-up Evaluations including H&P, Review of Systems, and toxicities
- Follow-up labs and dates
- Completion of QOL questionnaires
- Subject study withdrawal, date, and reason
- Concomitant medications, specifically PPIs and antiemetics, prescribed per protocol and if reportedly taken by subject

Information will be entered from source documents or from Case Report Forms which are formatted to capture data as it will be entered into the database. If information is entered from source documents directly into Oncospace, Case Report Forms can be printed out and signed or signed electronically.

The PI will be responsible for maintaining the clinical protocol and subjects' study charts, reporting adverse events, assuring that consent is obtained and documented, and reporting the status of the trial in continuing renewals submitted to their IRB and trail monitoring group(s) as per JHH protocol.

There will be password-protected limited access to the database in order to maintain privacy (See Confidentiality below).

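### The 7.2 addendum keeps late grade 2 gastritis, enteritis, fistula and ulcer off the AE log and Case Report Forms, although these events count in the primary endpoint and both toxicity decisions

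*Combined protocol and SAP*

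**What the plan says.** **What is counted.** Section 13.1.1 defines the primary endpoint as "late (>3 months after Linac based SBRT) grade 2 or greater gastritis, fistula, enteritis, or ulcer", together with other gastrointestinal toxicity from grade 3 upward, where attributable to SBRT. Section 13.4.2 uses the same events twice. The interim rule reads "Within 16 patients, if 7 or more patients have late grade 2 or greater gastritis, enteritis, fistula, ulcer"; other late GI events count from grade 3 upward, and at that number the trial stops. Section 12.2 repeats the rule. The final rule is that the null hypothesis of 40% stands "if 17 or more of the patients have late grade 2 or greater gastritis, enteritis, fistula, ulcer", again counting other late GI events from grade 3 upward; with 16 or fewer, the conclusion is that one-year late toxicity is below 40%.

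**What is recorded.** The 2014 addendum in 7.2 says adverse events are recorded in Mosaiq. It continues: "Any toxicity below CTCAE v4.0 grade 3 will not be reported on the Master AE Log or Case Report Forms". It then adds: "However, this information will be retained in patient charts". No event type is exempted.

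**Other relevant text.**
- Section 12.1.2 lists "Follow-up Evaluations including H&P, Review of Systems, and toxicities" among the data for Oncospace, with no grade limit. It allows entry directly from source records, and alternatively by way of "Case Report Forms which are formatted to capture data as it will be entered into the database".
- Section 12.1 names Oncospace and Mosaiq together as the study database.
- Section 13.3 plans toxicity tables by type and grade.
- Sections 12.2 and 13.3 send adverse events to the monitoring committee and the IRB, with no grade limit.
- Section 12.2 also says: "All outcome data (toxicity and efficacy) will be reviewed every 6 months by the Principal Investigator and key Co-Investigators".

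**The concern.** The addendum treats low-grade toxicity as expected background in a very sick population. That is reasonable for most events, but for these four, grade 2 is part of the outcome under test. Section 7.1 names duodenal and gastric ulcer as the major toxicity and says most cases are managed medically, so they are not a marginal part of the endpoint.

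As written, the rule takes these events off the two adverse-event records that the addendum names, and the plan does not say which other record feeds the counts. It also sits badly with the tables by type and grade in 13.3 and with the statements that all adverse events reach the monitoring committee.

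An event overlooked in a chart can act in one direction only. It makes the 16-patient stop less likely and the favorable final conclusion more likely. The stop is a patient-safety rule, and Cohort A is being re-irradiated. The six-monthly and committee reviews could also lack the grade 2 part of the endpoint.

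**Working it through.** **Inputs.** From 13.4.2, per cohort: first stage 16, total 60, stop at 7 or more of 16, favorable conclusion if 6 or fewer of 16 and then 16 or fewer of 60, null rate 0.40, alternative 0.20.

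**Step 1: reproduce the plan's figures.** Let X1 ~ Bin(16, p) and X2 ~ Bin(44, p), independent.
- P(stop at look) = P(X1 ≥ 7).
- P(conclude below 40%) = P(X1 ≤ 6 and X1 + X2 ≤ 16).
- At p = 0.40: stop 0.473 (plan 0.47); false conclusion 0.021 (plan 2%).
- At p = 0.20: favorable conclusion 0.908 (plan 91% power).

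The stated properties hold when every endpoint event is counted.

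**Step 2: allow for missed grade 2 events.** Events of grade 3 or more stay on the log and forms, so only grade 2 events are treated as missable. Let g be the share of endpoint patients whose worst event is grade 2, and m the fraction of those who are missed. The recorded rate at a true rate of 0.40 is

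q = 0.40 × (1 − g × m).

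**Step 3: a range for g.** The documents give no share for the four listed events. Two single-fraction series described in the protocol give an illustrative range:
- Section 3.3: 4% grade 2 and 9% grade 3 or more late toxicity, so g = 4/(4 + 9) = 0.308.
- Section 3.2: 7 patients with grade 2 or more, 2 of them grade 3 or more, so g = (7 − 2)/7 = 0.714.

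Both cover gastrointestinal toxicity more broadly than the four events, so applying them here is an assumption.

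**Step 4: results at a true rate of 40%.** The same formulas as in step 1, with p replaced by q:

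| Grade 2 events missed (m) | g | q | Stop at look | False conclusion below 40% |
|---|---|---|---|---|
| 0 | any | 0.400 | 0.473 | 0.021 |
| 10% | 0.308 | 0.388 | 0.432 | 0.032 |
| 10% | 0.714 | 0.371 | 0.379 | 0.056 |
| 25% | 0.308 | 0.369 | 0.372 | 0.060 |
| 25% | 0.714 | 0.329 | 0.249 | 0.181 |
| 100% (forms alone) | 0.308 | 0.277 | 0.126 | 0.477 |
| 100% (forms alone) | 0.714 | 0.114 | 0.001 | 0.999 |

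The calculation assumes that misses are independent between patients and that all patients are assessed to one year. The last two rows are a bound, reached only if charts, Mosaiq and source-document entry were all ignored.

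**The case against.** The strongest reply is that nothing is lost. Mosaiq holds adverse events with no grade limit, and 12.1.2 allows direct entry from source documents into Oncospace. The addendum restricts the log and the forms, not the database. Adverse events are evaluated at each follow-up visit in the study calendar. Records from outside are meant to reach the center: 6.4 says the team will requisition them, and footnote 4 of the calendar says they must be submitted. Charts are reviewed in monitoring (12.1) and at study completion (11.1.7).

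Most of this stands, and it is why the point is minor. A reader might infer that the plan has no source for the grade 2 events, or that the final test is almost bound to fail. The documents support neither. Several sources exist, and nothing says the counts use the forms alone.

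What remains is narrower. None of these provisions says that late grade 2 endpoint events are abstracted for the counts with grade, onset date and attribution, which the endpoint needs. The review in 11.1.7 concerns response and comes too late for the 16-patient look; the review in 12.1 is general monitoring. Section 12.1.2 also describes the Case Report Forms as matching the database, which leaves it unclear whether Oncospace would hold what the forms omit. Toxicity may be assessed by telephone (calendar footnote 13), which makes an explicit recording rule more useful.

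**Conclusion.** The concern holds as an inconsistency between a safety-reporting addendum and the primary endpoint. It is not a fault in the two-stage design, whose stated error rates reproduce. The plan excludes part of its primary endpoint from its adverse-event log and forms and does not state how that part is gathered for the two decisions.

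The direction of any error is certain; its size is not. With an assumed grade 2 share of 31% to 71% and a true rate of 40%, missing a tenth of grade 2 events leaves a 43% to 38% chance of stopping at the look and a 3% to 6% chance of the false conclusion, against 47% and 2.1% as planned. Missing a quarter gives 37% to 25% and 6% to 18%. No missed fraction can be taken from the documents, so these are illustrations and not estimates. The false conclusion would reach 48% or more only under a forms-only count, which the plan does not describe. Because the data can be recovered, severity is minor.

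**What to change.** Add an exception to the 7.2 addendum, for example:

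*Exception: gastritis, enteritis, fistula and ulcer of grade 2 or greater arising more than 3 months after SBRT belong to the primary endpoint. Each is entered on the Master AE Log and Case Report Form with grade, onset date and attribution to SBRT, including events learned of through local-provider records or by telephone. The 7-of-16 and 17-of-60 counts and the safety reviews use these entries. Such events in patients already treated are back-entered from charts and Mosaiq.*

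All other toxicity below grade 3 can stay in charts as now. The cost is a few sentences, a little extra logging for four event types, and a one-time back-entry. Sample size, boundaries and visits are unchanged. If staff already abstract these events, the amendment only documents current practice.
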